1.0 INTRODUCTION

The outcome of acute myeloid leukemia (AML) and myelodysplastic syndrome (MDS) in patients ≥ 55 years still remains unsatisfactory, with a low complete remission (CR) rate and poor overall survival (OS) due to a variety of reasons including increased incidence of poor-risk cytogenetics, increased activation of RAS, Src, and TNF pathways and intrinsic resistance of leukemic blasts to therapeutic agents. The 30-day induction mortality is also high and ranges from 10-50% and this is due to prolonged pancytopenia, febrile neutropenia and other systemic side effects that burden the already aging patient with comorbidities. [1-3]. Allogeneic stem cell transplantation (alloSCT) has curative potential; however, it is associated with severe graft-versus-host disease (GVHD), infections, and other treatment related morbidities or mortality for a high proportion of elderly patients [4, 5]. Thus, recent work has centered on less toxic ways to manipulate donor cells to achieve antitumor benefits.

A pilot study performed in China in elderly patients with AML treated with conventional chemotherapy followed by infusion of human leukocyte antigen (HLA) mismatched G-CSF mobilized peripheral blood stem cell infusion (G-PBSC) reported higher CR and disease-free-survival (DFS) rates, faster neutrophil and platelet recovery, and no GVHD or increase in treatment-related mortality [6]. Interestingly, although no patients exhibited full or mixed chimerism, donor microchimerism was monitored and observed in all four women who had male donors (sons or brothers). This may be due to long-term maternal-fetal microchimerism, and studies of HLA-haploididentical allo-SCT have shown improved outcomes after transplantation from noninherited maternal antigen (NIMA) mismatched donors [7]. Improved responses after HLA-mismatched G-PBSC infusion may also be due to natural killer (NK) cells: infusion of haploididentical NK cells from killer immunoglobulin-like receptor (KIR) ligand mismatched donors have shown alloreactivity against leukemia [8, 9]. Because induction and consolidation chemotherapy followed by infusion of HLA-haploididentical cells, or donor lymphocyte infusion (DLI), is a new procedure, our first priority is to replicate the above study as a Phase I trial to assess safety.

Our primary hypothesis is that chemotherapy followed by infusion of HLA-haploididentical DLI from KIR-ligand mismatched donors is a safe procedure that will not cause GVHD or increased treatment-related mortality. We further believe that this will improve outcomes of elderly patients with high-risk AML or MDS compared to chemotherapy alone, and that this benefit will be even greater in donor-recipient pairs that share maternal-fetal microchimerism or NIMA-mismatch. A large part of this trial will include immune function assays as well as assessments of efficacy, toxicity, and GVHD. Because this therapy may be a tolerable alternative to alloHSCT for elderly patients, we will validate functional measurements (e.g. Comprehensive Geriatric Assessment (CGA)) with biologic correlates (cytokine and genomic profiles) and clinical outcomes.

2.0 STUDY OBJECTIVES

2.1 Primary Objective

2.1.1 Evaluate the safety of HLA-haploididentical DLI combined with conventional induction and consolidation chemotherapy in terms of unacceptable toxicity as defined in section 7.0.

2.1.2 Evaluate the efficacy of HLA-haploidentical DLI combined with conventional induction and consolidation chemotherapy in terms of one-year DFS.

2.1.3 Validate the use of the CGA in elderly AML and MDS patients undergoing cellular therapy

2.2 Secondary Objectives

2.2.1: Evaluate incidence and severity of acute GVHD.

2.2.2: Evaluate incidence and severity of other adverse events.

2.2.3: Evaluate efficacy with respect to CR and OS.

2.2.4: Evaluate immune recovery.

2.2.5: Evaluate hematopoietic recovery.

3.0 BACKGROUND

3.1 High-Risk AML and MDS in the Elderly

Elderly AML and MDS patients have long been known to have much worse rates of CR, DFS, and OS compared to their younger counterparts [1, 3]. The CR rates in elderly AML patients treated with standard induction chemotherapy (7+3, i.e. 7 days of cytarabine and 3 days of anthracycline) is ~30-65%, with more than half of these patients relapsing within six months [1, 10], and survival in high-risk MDS is only 26 months vs. 141 months for very low risk[11]. In part, this is because elderly patients are less likely to have favorable cytogenetics: an analysis of 1065 elderly patients with AML found 7% to have favorable cytogenetics, 73% intermediate, and 20% poor, with complete remission rates of 72%, 53-63%, and 26% respectively, and five-year overall survival rates of 34%, 10-15%, and 2% respectively [12]. However, even with favorable cytogenetics, patients older than 65 have poor outcomes with <10% two-year overall survival [1].

3.2 Stem Cell Transplant for Elderly High-Risk AML and MDS

Nonmyeloablative or reduced intensity conditioning (RIC) allogeneic stem cell transplantation (alloSCT) does have curative potential for elderly patients with AML and MDS; however, it is associated with severe graft-versus-host disease (GVHD), infections, and organ toxicity that may lead to unacceptably high rates of morbidity and mortality [4, 5, 13]. Further, the lack of an available human leukocyte antigen (HLA)-matched donor remains a major obstacle for many patients. Haploidentical transplantation may provide a larger pool of available donors, but it is limited by significant morbidity and mortality (e.g., GVHD and infections) [14]. DLI can also mediate strong graft-versus-leukemia (GVL) effects but may be associated with severe GVHD and delayed neutrophil recovery after alloSCT [15, 16].

3.3 Graft versus Leukemia (GVL) Effect

Most patients with hematologic malignancies are not cured with standard chemotherapy. Outcomes are improved by alloSCT, which can induce an immunologic effect against the cancer. In patients with leukemia, this has been termed a graft versus leukemia effect. Evidence for this includes:

1. temporal relationship between graft versus host disease and hematologic remission [17]
2. reduced incidence of leukemic relapse after alloSCT compared to syngeneic SCT [18]
3. reduced incidence in leukemic relapse in alloSCT recipients who do develop GVHD compared to those who do not [19]

Multiple laboratory studies have been published in support of this clinical data as well. Tumor specific antigens, histocompatibility antigens, and killer immunoglobulin receptors (KIR) may play a role through direct cell contact, activating NK cells, or indirect production of cytotoxic cytokines (interferon, TNF-alpha, IL-2, IL12).

3.4 Donor Leukocyte Infusions as a way to Induce GVL Effect

Recent work with patients who have relapsed or have persistent disease post-alloSCT has centered on using donor leukocyte infusions to stimulate more graft versus tumor effect and re-attain remission [20, 21]. Reports are growing of clinically significant results in various types of malignant and non-malignant processes, and it is now the standard of care to proceed with donor leukocyte infusions in patients who have relapsed disease post allogeneic transplantation [22].

For non-selected DLIs, donors are asked to provide peripheral blood progenitor cells in the same manner as for transplantation; these are then transfused through a peripheral intravenous line into the recipient. Typically, somewhere between 10^5 to 10^6 CD3+ T cells/kg recipient weight are infused over 1 to 2 days every 4-12 weeks, though there is no set standard. Although higher doses are associated with increased anti-tumor immunity, they are also associated with increased GVHD. The time between infusions allows for observation and management of pancytopenia, the anticipated side effect if significant graft versus tumor effects is encountered along with suppressive effects on the patient's innate hematopoiesis. Immunosuppressive agents are continued during leukocyte infusions; however, if clinically significant graft versus host disease does occur, treatment may be initiated to control the degree of response at that time.

3.5 NK Alloreactivity

Donor-versus-recipient NK alloreactivity has emerged as a crucial factor for the outcome of haploidentical SCT [8]. Alloreactivity is mediated by KIR-ligand mismatch between donor and recipient [23]. Ruggeri et al showed a low relapse risk for patients with acute myeloid leukemia transplanted from NK-alloreactive donors [9]. Further, adoptive transfer of alloreactive haploidentical NK cells has been shown to be safe and effective in treatment

Chemo with Adoptive Haplo DLI

of AML [24, 25]. NK-enriched DLI may also improve outcomes and immune recovery [26].

3.6 NIMA and Maternal-Fetal Microchimerism

Outcomes after HLA-haploidentical allo-SCT are better when using the patient's mother as the donor compared to the father [7, 27, 28]. This is thought to be secondary to in-utero exposure of NIMA, leading to the establishment of long-term maternal-fetal microchimerism, which can be found in 40% of adults [29] and lead to both tolerogenic as well as sensitizing effects [30, 31]. One study by Stern et al found the five-year event-free survival rate was 50% in patients who had transplants from their mother versus 11% for those who had transplants from their father, in large part due to reduced incidence of relapse, thought secondary to improved graft-versus-leukemia[27]. Maternal-fetal microchimerism may also mediate a graft-versus-leukemia effect in cord blood transplantation [32]. Thus, adoptive transfer of cells from mother to child or child to mother may improve outcomes.

3.7 Infusion of HLA-mismatched peripheral blood stem cells in elderly AML

A recent Chinese study reported that mice infused with a high dose of G-CSF–mobilized allogeneic spleen cells ($3-12 \times 10^7$) after cytarabine chemotherapy exhibited rapid hematopoietic recovery and persistent microchimerism without GVHD despite absence of GVHD prophylaxis and immunosuppressive treatment [6]. On the basis of these observations, they designed a clinical control study to investigate the effects of G-PBSC combined with conventional induction and intensive postremission chemotherapy on outcomes of AML in elderly patients. Fifty-eight AML patients aged 60-88 years were randomly assigned to receive induction chemotherapy with cytarabine and mitoxantrone (control group; n=28) or same chemotherapy plus HLA-mismatched G-PBSCs (G-PBSC group; n=30) (median CD3+ cell dose: 0.9×10^{10} CD3+ cells/kg recipient body weight). Patients who achieved CR received another 2 cycles of postremission therapy with intermediate-dose cytarabine plus G-PBSCs. The complete remission rate was significantly higher in the G-PBSC group than in the control group (80.0% vs. 42.8%; $P = .006$). The median recovery times of neutrophils and platelets in the G-PBSC group were 11 days and 14.5 days, respectively, and 16 days and 20 days in the control group. The 2 year probability of disease-free survival was significantly higher in the G-PBSC group than in the control group (38.9% vs. 10.0%; $P = .01$). No graft-versus-host disease was observed in any patient.

Given that none of these patients experience engraftment, yet there was a significant improvement in disease free survival, we hypothesize that these results were due to infused donor lymphocytes rather than CD34+ stem cells. As a result, G-PBSC may not be necessary and HLA-haploidentical DLI would suffice.

3.8 Geriatric assessment

To better understand the mechanisms that contribute to the poor prognosis of

Chemo with Adoptive Haplo DLI

elderly AML patients, our laboratory has demonstrated that differences in the underlying biology (higher probability of Src, TNF, and RAS pathway activation in elderly AML patients as compared to their younger counterparts) contribute to poor survival[33]. We will build on this knowledge by using the CGA to improve our clinical assessment of functional status in elderly AML and MDS patients to predict responses to and toxicity from induction therapy as well as mortality and correlate these results with biologic markers of frailty using cytokine and genomic profiles.

4.0 RATIONALE

Elderly patients with high-risk AML and MDS respond very poorly to conventional induction regimens and have high relapse rates. AlloSCT is one way of decreasing relapse but at the cost of toxicity and GVHD. Infusion of HLA-haploididentical stem cells may provide an alternate means of inducing a graft-versus-leukemia effect with less toxicity. This may be mediated by NK-alloreactivity and potentiated by maternal-fetal microchimerism. Our trial will attempt to confirm the safety and efficacy of the Chinese study in an attempt to improve 2-year survival in elderly high-risk AML and MDS patients, with minimal toxicity and GVHD, with a focus on immunological correlates and function in an attempt to further understand the mechanism of this phenomenon.

We have selected the dose of $1 \times 10E8$ CD3+ cells/kg recipient body weight based on the success of this dose in the study by Guo et. al.[6] and the use of $1 \times 10E8 - 2 \times 10E8$ CD3+ cells/kg recipient body weight by Colvin et. al. in a similar study[34]. In both the Guo and Colvin studies, GVHD was not seen at this dose.

5.0 ELIGIBILITY CRITERIA

Laboratory, bone marrow biopsy, and radiographic evaluation to determine eligibility should be done within 4 weeks of registration. Baseline staging studies not needed for eligibility but used to assess disease prior to transplantation may be performed up to 8 weeks before registration.

5.1 Patient Eligibility

1. Subjects must have their diagnosis of high-risk AML or high-risk MDS confirmed by pathologic review of bone marrow biopsy according to WHO guidelines [35] (see below for definitions of high-risk)
 - We will define patients as high risk AML and thus eligible if they meet one or more of the following criteria:
 - a. Secondary AML (from underlying MDS or therapy related)
 - b. Presence of complex cytogenetic abnormalities (≥ 3 cytogenetic abnormalities), all monosomies, del 5q, del 7q, inv3, t(3;3), t(6;9), t(9;22), abn 11q23 (excluding t(9;11))[36]
 - c. FLT3-ITD mutation positive
 - d. Age ≥ 65 years given poor outcomes even with favorable

Chemo with Adoptive Haplo DLI

cytogenetics[1]

- We will define subjects as high risk MDS and thus eligible if they have a MD Anderson Comprehensive Cancer MDS Risk Score ≥ 9 [3]
- 2. Subjects must have ECOG Performance status of 0,1,or 2; if ECOG 2, they must also have a Charlson comorbidity index of ≤ 5 .[37]
- 3. Subjects must be ≥ 55 years of age
- 4. Subjects should have a potential 3-5/6 HLA-matched related haploidentical donor that will be evaluated for eligibility to provide DLI.
- 5. Patient should be able to provide informed consent
- 6. Subjects must have a MUGA and /or ECHO or cardiac MR. The required minimum standards include MUGA or ECHO or cardiac MR showing an EF of 40%. Those with an EF 40-49% must also have a cardiologist consult and assist with management.
- 7. PFTs with DLCO are conditional for subjects at the discretion of the physician. The required minimum standards for those who have PFTs include DLCO of 40%. Those with DLCO of 40-49% must have a pulmonologist consult and assist with management.
- 8. Subjects of all genders and races are eligible

5.2 Exclusion criteria

1. Pregnant or lactating women.
2. Patients with other major medical or psychiatric illnesses which the treating physician feels could seriously compromise tolerance to this protocol
3. Patients with known active CNS disease
4. Patients with acute promyelocytic leukemia (FAB M3)

5.3 Donor selection

1. Adult donors must be must be a HLA 3-5/6 related haploidentical match with the patient and must be capable of providing informed consent
2. Donors must not have any medical condition which would make apheresis more than a minimal risk, and should have the following:
 - a. Family members will be considered for donation if they do not have a history of known cardiac problem and do not have abnormal cardiac findings by physical examination. Those with a history of cardiac problems or abnormal cardiac findings by physical examination should undergo a stress evaluation or be evaluated by a cardiologist and deemed eligible to donate
 - b. Bilirubin and hepatic transaminases $\leq 2.5 \times$ ULN,
 - c. Adequate hematologic parameters including a hematocrit $> 35\%$ for males and 33% for females, white blood cell count of $\geq 3,000$, and platelets $\geq 80,000$.
 - d. FACT labs must be drawn within 7 days of collection and final test results available prior to infusion into the patient (copy of labs included in appendices). In the case of multiple donations from the donor, the FACT labs must be redrawn within 7 days of each initiation of apheresis (positive serologies are not repeated as they remain positive for lifetime but all other donor labs are performed as per the donor appendix sheet).

Chemo with Adoptive Haplo DLI

3. Females of childbearing potential should have a negative serum beta-HCG test within 1 week of beginning growth factor of choice

5.3.1 Donor selection algorithm

Preference is first given to:

- a. the best matched family member who meets other donor criteria, followed by
- b. age (younger donor preferred)
- c. KIR reactivity according to the following rules:
 - i. If a recipient is missing HLA-C group2 ligand, a preferable donor has an inhibitory KIR to HLA-C group2 ligand (KIR2DL1)
 - ii. If a recipient is missing HLA-A3/A11 ligand, a preferable donor has an inhibitory KIR to HLA-A3/A11 ligand (KIR3DL2)
 - iii. If a recipient is missing HLA-Bw4 ligand, a preferable donor has an inhibitory KIR to HLA-Bw4 ligand (KIR3DL1)
 - iv. A preferable donor has more than one inhibitory KIR (2DL1/2/3, 3DL1/2) without corresponding ligand in a recipient, followed by
- d. CMV negativity
- e. NIMA mismatch over NIPA mismatch

6.0 TREATMENT PLAN

6.1 Prior to starting therapy

Prior to enrollment, potential subjects will have a complete history and physical examination performed as well as the following required lab tests: CBC with differential (auto or manual), creatinine, AST, ALT, total bilirubin, and bone marrow biopsy with cytogenetics and molecular mutation studies. These should all be completed within four weeks prior to enrollment. Cardiopulmonary testing as per section 5.1 must be completed within eight weeks. Other recommended tests (not required but helpful for final analysis) include: CMV immune screen, LDH, uric acid, alkaline phosphatase, sodium, potassium, chloride, bicarbonate, glucose, total protein, albumin, calcium, magnesium, phosphorous.

If a potential subject is awaiting the above required lab tests to assess suitability for enrollment (e.g. normal cytogenetics and FLT-3 mutation testing), and if WBC is elevated and/or rising, hydrea or leukapheresis may be initiated at the discretion of the treating physician.

6.2 Donor priming and apheresis

Exam and laboratory analyses will follow current Foundation for the Accreditation of Cellular Therapy (FACT) standard of care accreditation requirements for cellular therapy practices.

6.2.1 Mobilization

Recommended mobilization includes G-CSF 8 mcg/kg subcutaneously twice daily for 4 days prior to stem cell collection and continuing until pheresis is

Chemo with Adoptive Haplo DLI

completed. Dose should be rounded to nearest vial size. Alternative mobilization strategies may be employed at the investigator's discretion.

6.2.2 Collection of cells

General guidelines (though may be altered for program standards and evolving stand of care without being a violation): The goal is to collect 3×10^8 CD3+ cells/kg recipient body weight. If, after a maximum of 2 leukaphereses, the target collection is not reached, the treating physician may decide to proceed with a third collection after re-discussion with the patient and donor. If the goal dose is not reached, infusion will still take place if a minimum of 2×10^8 CD3+ cells are collected, and recovery will be monitored as the patient will normally have autologous recovery.. The infusion schedule will be modified as below (6.3.4). Leukapheresed cells will be processed and frozen in the cryopreservation lab according to standard procedures, unless they are to be immediately infused into the patient after processing (e.g. freshly collected cells to be given following induction).

The donor lymphocyte infusion meets criteria to be regulated solely as HCT/P instead of a drug/biologic. There is no manipulation of donor cells and the donor is a first or second degree relative.

6.2.3 Storage and processing

The stem cells are processed in the Duke University Medical Center Stem Cell Laboratory and infused to the donor following the standard laboratory procedures for allogeneic stem cell infusions. Freshly collected cells will be used in the first course of treatment and donor cells will be divided into aliquots and cryopreserved in liquid nitrogen for subsequent infusions. Each infusion of the cells will be performed 1 day following each chemotherapy regimen and that day will be counted as 'day 0'. The target dose of CD3+ cells is 1×10^8 cells/kg (the collection goal of 3×10^8 CD3+ cells/kg is to obtain 1 aliquot of 1×10^8 CD3+ cell/kg for each of induction and consolidation2, with 1×10^8 CD3+ cell/kg saved in case of need for re-induction). If only $2-3 \times 10^8$ CD3+ cell/kg is collected, then cells will only be given with IND1 and CON2 (IND2 may still be done, but cells will not be given). We will also monitor the total number of mononuclear, CD34+, CD3-CD16+CD56+ (NK) cells, CD3+CD16+CD56+ (NKT) cells, and gamma-delta T-cells infused, but the infusion dose will be calculated around CD3+ population.

6.3 Treatment Plan

6.3.1 Induction therapy

Eligible subjects will receive induction chemotherapy with idarubicin (12 mg/m^2 intravenously for 3 days) and cytarabine (100 mg/m^2 intravenously for 7 days) starting Day 1 and ending Day 7 as described in Figure 1. Patients 80 years or older may receive 2 and 5 days of idarubicin and cytarabine respectively starting Day 1 and ending Day 5 (optional, at physician discretion). HLA-mismatched DLI will be administered Day 9

Chemo with Adoptive Haplo DLI

(DLI will occur on Day 7 for 5+2 regimen), approximately 24-48 hours following completion of chemotherapy at a dose of 1×10^8 CD3+ cells; however, due to logistics of planning infusions with staffing, donor availability, weekends/holidays, etc., it may be necessary to postpone cell infusion up to 96 hours, which will be allowed without being considered a protocol violation.

Subjects who experience no remission or partial remission will receive a second course of the identical induction chemotherapy (IND2). IND2 should include 7+3+DLI as per IND1, but if cells are not available as per 6.2.3, chemotherapy alone can be given without being considered a protocol violation.

Given the time constraints presented by the need to start induction chemotherapy as soon as possible, in some cases, it may not be logistically possible to administer cells with induction (e.g., obtaining insurance approval for clinical trial/DLI may take a while, and approval may not be back in time for a patient to receive cells). In these cases, patients would just receive standard induction chemotherapy and cells would be administered after CON1 in addition to CON2 (see below). Timing of correlative laboratory studies will be adjusted to match cell infusion. Guo et al. have reported improved outcomes with high cell doses (1×10^8 CD3+ cells/kg) administered after consolidation, even in patients who receive standard induction chemotherapy without cells.¹

¹Guo M, Hu KX, Liu GX, Yu CL, Qiao JH, Sun QY, Qiao JX, Dong Z, Sun WJ, Sun XD, Zuo HL, Man QH, Liu ZQ, Liu TQ, Zhao HX, Huang YJ, Wei L, Liu B, Wang J, Shen XL, Ai HS. HLA-mismatched stem-cell microtransplantation as postremission therapy for acute myeloid leukemia: long-term follow-up. *J Clin Oncol.* 2012 Nov 20;30(33):4084-90. doi: 10.1200/JCO.2012.42.0281. Epub 2012 Oct 8.

[figure not shown]

Figure 1: Chemotherapy followed by adoptive transfer of HLA-haploidentical donor lymphocytes. Patients will receive induction chemotherapy followed by cell infusion, and then 2 rounds of consolidation chemotherapy followed by cell infusion. If patients do not achieve complete remission after the first round of induction, they may undergo a second round. Ara-C, cytarabine; Cells, adoptive transfer of HLA-haploidentical donor lymphocytes; CON1, first consolidation; CON2, second consolidation; CR, complete remission; Ida, idarubicin; IND1, first induction chemotherapy; IND2, second induction chemotherapy; NR, no response

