6.3.2 Postremission treatment

Subjects who achieve a CR will receive 2 further courses of cytarabine postremission chemotherapy (consolidation) at 1.0 g/m^2 for 6 dosages followed by HLA-mismatched DLI after the second consolidation. Cytarabine will be given twice daily at 12 hour intervals on days 1, 3, and 5; HLA-mismatched DLI will be administered the day following the completion of the second consolidation (day 7) at a dose of $1 \times 10^8 \text{ CD3+ cells}$, although as above, a 24-96 hour interval between completion of chemotherapy and infusion of cells will be allowed for logistical reasons without being considered a protocol violation.

No cells will be given after the first consolidation, as chemotherapy given with the second consolidation will likely kill any cells infused after the first consolidation (i.e. infusion of cells after the first consolidation would be costly and low-yield) (Note that while this argument could also be applied to cells infused after induction, Guo et al. showed an improvement in the CR rate from 40% to 80% with the use of cells with induction, which is why we plan to use cells after induction in this trial).

The timing of consolidation typically takes place after count recovery, around 6-12 weeks after induction, following standard protocols and timing for cytarabine consolidation.

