6.3.4 DLI

Allogeneic DLI will be collected from the donor as described in section 6.2.2. The allogeneic DLI will be infused as per current practice.

Subjects will be given premedications including Benadryl 25 mg IV, and Acetaminophen 650 mg po prior to infusion. Hydrocortisone is used at the physician's discretion.

If needed, modifications to the infusion rate may be made as per standard practice.

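### The infusion dose in 6.3.1 and 6.3.2 and the minimum collection in 6.2.2 omit the per-kg unit that the rest of the protocol shows is intended

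*Combined protocol and SAP*

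**What the plan says.** The two sections that order the infusion give a plain cell count. In 6.3.1 the cells are given "approximately 24-48 hours following completion of chemotherapy at a dose of 1×10^8 CD3+ cells". Section 6.3.2 repeats the flat 1×10^8 CD3+ cells for the infusion after the second consolidation. On collection, 6.2.2 first sets a per-kg target: "The goal is to collect 3×10^8 CD3+ cells/kg recipient body weight". It then gives the fallback without the unit: "infusion will still take place if a minimum of 2×10^8 CD3+ cells are collected". For that fallback it adds "The infusion schedule will be modified as below (6.3.4").

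Section 6.3.4 covers infusion practice and premedication. It states no dose and no schedule, and it points back: "Allogeneic DLI will be collected from the donor as described in section 6.2.2".

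Elsewhere the unit is present. Section 4.0 selects 1×10^8 CD3+ cells per kg of recipient body weight. Section 6.2.3 sets the target dose per kg and explains that the collection goal provides "1 aliquot of 1×10^8 CD3+ cell/kg for each of induction and consolidation2", with a further 1×10^8/kg held for a possible re-induction. It also holds the actual short-collection rule: at 2 to 3×10^8/kg, cells go with the first induction and the second consolidation only.

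**The concern.** The cell dose is the experimental treatment, and 6.3.1 and 6.3.2 are the sections a treating team would follow. As written they order a fixed count that falls short of the selected dose by a factor equal to the recipient's weight in kg. The flat minimum in 6.2.2 would also allow infusion from a collection far too small for the two planned doses, whereas 6.2.3 has no schedule for anything below 2×10^8/kg.

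Two features make the slip harder to notice. First, the literal dose does not look absurd: section 3.4 describes usual DLI practice as "somewhere between 10^5 to 10^6 CD3+ T cells/kg recipient weight are infused", and the flat dose lands at or slightly above the top of that range. Second, the cross-reference for a short collection leads to a section with no rule in it, while the real rule stands in 6.2.3.

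The risk is under-dosing, and mixed exposure among at most 21 evaluable patients. It is not extra exposure to graft-versus-host disease.

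**Working it through.** **Which unit is intended.** Inputs: aliquot size 1×10^8/kg (6.2.3), collection goal 3×10^8/kg (6.2.2 and 6.2.3), lower end of the short-collection range 2×10^8/kg (6.2.3).

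- Induction + second consolidation + reserve: 3 × 1×10^8/kg = 3×10^8/kg. This reproduces the plan's goal.
- Induction + second consolidation only: 2 × 1×10^8/kg = 2×10^8/kg. This reproduces the lower end of the 6.2.3 range, and it is the same figure as the 6.2.2 minimum with its unit restored.
- On the flat reading the plan does not fit together. At 70 kg the goal is 3×10^8 × 70 = 2.1×10^10 cells, and three flat doses would use 3×10^8 of them, or 1.4%.

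Section 6.2.3 says only per kg; that the weight is the recipient's comes from 4.0 and from the goal sentence in 6.2.2.

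**Size of the literal error.** The documents give no body weights, so w = 50, 70 and 100 kg are assumptions. The flat dose per kg is 1×10^8 / w. The shortfall is 1×10^8 divided by that, which equals w. Two aliquots need 2×10^8 × w cells, and the flat minimum covers 2×10^8 / (2×10^8 × w) = 1/w of them.

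| Assumed weight | Flat dose per kg | Below 1×10^8/kg by | Cells needed for two aliquots | Flat minimum as share |
|---|---|---|---|---|
| 50 kg | 2.0×10^6 | 50-fold | 1.0×10^10 | 2.0% |
| 70 kg | 1.4×10^6 | 70-fold | 1.4×10^10 | 1.4% |
| 100 kg | 1.0×10^6 | 100-fold | 2.0×10^10 | 1.0% |

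Against the 10^5 to 10^6/kg in section 3.4, the literal dose is between one and two times the upper end.

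**A separate, minor discrepancy.** Section 3.7 reports the earlier randomized study's median dose as 0.9×10^10 CD3+ cells/kg, while 4.0 credits that study with success at 1×10^8/kg. The ratio is 0.9×10^10 / 1×10^8 = 90. If 0.9×10^10 were a total count, it would be 1.8, 1.3 and 0.9×10^8/kg at 50, 70 and 100 kg, close to the figure in 4.0. That is only a possibility; the documents cannot settle it. The other two dose citations (1 to 2×10^8/kg in 4.0, and 1×10^8/kg for the post-remission study in 6.3.1) agree with the chosen dose.

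**The case against.** The best reply is that a careful reader cannot go wrong. Section 6.2.3 states the target per kg and divides the product into per-kg aliquots, so the laboratory would already have prepared the right amount before anyone reads 6.3.1. Section 6.3.1 itself refers to 6.2.3 and, further down, cites a per-kg dose in support. In 6.2.2 the flat minimum follows shortly after the per-kg goal and can be read as shorthand. Processing takes place in one institutional laboratory. The range in 3.4 describes infusions for relapsed or persistent disease after transplantation, which is a different setting. Section 6.2.2 is also introduced as general guidelines.

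Most of this stands, and it limits the point: the intended dose can be recovered, and the harm is possible rather than shown. It does not remove the error. The guideline label covers collection, not the infusion orders in 6.3.1 and 6.3.2. The reference to 6.2.3 within 6.3.1 concerns whether cells are available for a second induction, not the dose. The short-collection reference in 6.2.2 still leads to a section without a rule. It is also fair to say that the discrepancy between 3.7 and 4.0 concerns background on another study and sets no dose here; it is kept only as a minor check.

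**Conclusion.** The concern holds. Three operative figures (the two infusion orders and the minimum collection) have lost their per-kg unit, and one cross-reference is wrong. The intended value is not in doubt: 1×10^8 CD3+ cells per kg of recipient body weight per infusion, with a minimum of 2×10^8/kg. Taken literally, the dose would be 50 to 100 times too low at the assumed 50 to 100 kg; these weights serve only to show scale. No design figure is affected: the two-stage toxicity boundaries and the one-year disease-free survival test do not use the dose. It should be fixed because the error sits in the administration instructions for the experimental treatment.

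**What to change.** - In 6.3.1 and 6.3.2, state the dose as 1×10^8 CD3+ cells/kg recipient body weight.
- In 6.2.2, state the minimum as 2×10^8 CD3+ cells/kg recipient body weight, and point the short-collection reference to 6.2.3 instead of 6.3.4.
- Minor: check the median dose in 3.7 against its source so that 3.7 and 4.0 agree.

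The main correction costs three unit insertions and one changed cross-reference. Sample size, stopping rule and analysis stay as they are.
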